8.3.1 Physical Examinations

8.3.1.1 Full Physical Examination

The investigator or qualified designee (consistent with local requirements) will perform a complete physical examination during the screening period per institutional standard. Height and weight will also be measured and recorded. Clinically significant abnormal findings should be recorded as medical history.

Time points for full physical exams are described in Section 1.3. After the first dose of study intervention, new clinically significant abnormal findings should be recorded as AEs.

Investigators should pay special attention to clinical signs related to previous serious illnesses.

8.3.1.2 Directed Physical Examination

For cycles that do not require a full physical examination as defined in Section 1.3, the investigator or qualified designee (consistent with local requirements) will perform a brief directed physical examination (per institutional standard) as clinically indicated before study intervention administration. New clinically significant abnormal findings should be recorded as AEs.

Investigators should pay special attention to clinical signs related to previous serious illnesses.

8.3.2 Vital Signs

- Temperature, pulse rate, RR, and BP will be assessed by institutional standard.
- BP and pulse measurements will be assessed per institutional standard with a completely automated device. Manual techniques will be used only if an automated device is not available.
- BP and pulse measurements should be preceded by at least 5 minutes of rest for the participant in a quiet setting without distractions.

- Vital signs will be measured in a semi-supine position after 5 minutes rest and will include temperature, systolic and diastolic BP, and pulse and RR.

8.3.3 Electrocardiograms

A standard 12-lead ECG will be obtained and reviewed by an investigator or medically qualified designee (consistent with local requirements) as outlined in the SoA using an ECG machine that automatically calculates the HR and measures pulse rate, QRS, and QT intervals.

8.3.4 Performance Assessments

8.3.4.1 Eastern Cooperative Oncology Group Performance Status

The ECOG Performance Status is standardized criteria to measure how cancer impacts level of functioning (performance status) in terms of ability to care for oneself, daily activity, and physical ability (walking, working, etc.) with Grades 0 to 5.

The investigator or qualified designee will assess ECOG status (see Appendix 8) at Screening, before the administration of each dose of study intervention, at the End of Treatment Visit, and at the 30 day Safety Follow-up Visit, as specified in the SoA (Section 1.3).

8.3.5 Clinical Safety Laboratory Assessments

Refer to Appendix 2 for the list of clinical laboratory tests to be performed and to the SoA for the timing and frequency.

- The investigator or medically qualified designee (consistent with local requirements) must review the laboratory report, document this review, and record any clinically relevant changes occurring during the study in the AE section of the CRF. The laboratory reports must be filed with the source documents. Clinically significant abnormal laboratory findings are those which are not associated with the underlying disease, unless judged by the investigator to be more severe than expected for the participant's condition.
- All protocol-required laboratory assessments, as defined in Appendix 2, must be conducted in accordance with the Laboratory Manual or Procedure Document and the SoA.
- If laboratory values from nonprotocol-specified laboratory assessments performed at the institution's local laboratory require a change in study participant management or are considered clinically significant by the investigator (eg, SAE or AE or dose modification), then the results must be recorded in the appropriate CRF (eg, SLAB).
- For any laboratory tests with values considered clinically significantly abnormal during participation in the study or within 30 days after the last dose of study intervention, every attempt should be made to perform repeat assessments until the values return to normal or baseline or if a new baseline is established as determined by the investigator.

Details regarding specific laboratory assessments to be performed in this study are provided below. The total amount of blood/tissue to be drawn/collected over the course of the study (from prestudy to poststudy visits), including approximate blood/tissue volumes drawn/collected by visit and by sample type per participant can be found in the Laboratory Manual or Procedure Document. Refer to the SoA (Section 1.3) for the timing of laboratory assessments.

8.3.5.1 Laboratory Safety Evaluations (Hematology, Chemistry and Urinalysis, Etc.)

Laboratory tests for hematology, chemistry, and urinalysis are specified in Appendix 2 along with tests for thyroid function, cortisol, and ACTH.

8.3.5.2 Pregnancy Test

All women who are being considered for participation in the study, and who are not surgically sterilized or postmenopausal, must be tested for pregnancy within 24 hours (urine) or 72 hours (serum) prior to the first dose of study intervention. If a urine test is positive or not evaluable, a serum test will be required. Participants must be excluded/discontinued from the study in the event of a positive test result. Repeated pregnancy test (such as monthly testing) may be conducted if required by local regulation.

8.3.6 Pregnancy Testing

- Pregnancy testing:
 - Pregnancy testing requirements for study inclusion are described in Section 5.1.
 - Pregnancy testing (urine or serum as required by local regulations) should be conducted prior to every cycle during intervention.
 - Pregnancy testing (urine or serum as required by local regulations) should be conducted at the end of relevant systemic exposure.
 - Additional serum or urine pregnancy tests may be performed, as determined necessary by the investigator or required by local regulation, to establish the absence of pregnancy at any time during the subject's participation in the study.

8.4 Adverse Events, Serious Adverse Events, and Other Reportable Safety Events

The definitions of an AE or SAE, as well as the method of recording, evaluating, and assessing causality of AE and SAE and the procedures for completing and transmitting AE, SAE, and other reportable safety event reports can be found in Appendix 3.

Progression of the cancer under study is not considered an AE as described in Section 8.4.6 and Appendix 3.

Adverse events, SAEs, and other reportable safety events will be reported by the participant (or, when appropriate, by a caregiver, surrogate, or the participant's legally authorized representative).

The investigator and any designees are responsible for detecting, documenting, and reporting events that meet the definition of an AE or SAE as well as other reportable safety events. Investigators need to document if an SAE was associated with a medication error, misuse, or abuse.

Investigators remain responsible for following up AEs, SAEs, and other reportable safety events for outcome according to Section 8.4.3. The investigator, who is a qualified physician, will assess events that meet the definition of an AE or SAE as well as other reportable safety events with respect to seriousness, intensity/toxicity, and causality.

8.4.1 Time Period and Frequency for Collecting AE, SAE, and Other Reportable Safety Event Information

All AEs, SAEs, and other reportable safety events that occur after the participant provides documented informed consent, but before intervention allocation, must be reported by the investigator if the participant is receiving placebo run-in or other run-in treatment, if the event causes the participant to be excluded from the study, or is the result of a protocol-specified intervention, including, but not limited to washout or discontinuation of usual therapy, diet, or a procedure.

- All AEs from the time of intervention allocation through 30 days after cessation of study intervention must be reported by the investigator.
- All AEs meeting serious criteria, from the time of intervention allocation through 90 days after cessation of study intervention or 30 days after cessation of study intervention if the participant initiates new anticancer therapy, whichever is earlier, must be reported by the investigator.
- All pregnancies and exposure during breastfeeding, from the time of intervention allocation through the time required to eliminate systemic exposure after cessation of study intervention as described in Section 5.1, or 30 days after cessation of study intervention if the participant initiates new anticancer therapy must be reported by the investigator.
- Additionally, any SAE brought to the attention of an investigator at any time outside the time specified above must be reported immediately to the Sponsor if the event is considered related to study intervention.

Investigators are not obligated to actively seek AEs or SAEs or other reportable safety events in former study participants. However, if the investigator learns of any SAE, including a death, at any time after a participant has been discharged from the study, and the investigator considers the event to be reasonably related to the study intervention or study participation, the investigator must promptly notify the Sponsor.

All initial and follow-up AEs, SAEs, and other reportable safety events will be recorded and reported to the Sponsor or designee within the time frames as indicated in [Table 8](#).

Table 8 Reporting Periods and Time Frames for Adverse Events and Other Reportable Safety Events

Type of Event	Reporting Period: Consent to Randomization/ Allocation	Reporting Period: Randomization/ Allocation Through Protocol-specified AE Collection Period	Reporting Period: After the Protocol-specified AE Collection Period	Time Frame to Report Event and Follow-up Information to Sponsor
NSAE	Report if: – due to protocol-specified intervention – causes exclusion – participant is receiving placebo run-in or other run-in treatment	Report all	Not required	Per data entry guidelines
SAE including Cancer and Overdose	Report if: – due to protocol-specified intervention – causes exclusion – participant is receiving placebo run-in or other run-in treatment	Report all	Report if: – drug/vaccine related. (Follow ongoing to outcome)	Within 24 hours of learning of event
Pregnancy/Lactation Exposure	Report if: – participant has been exposed to any protocol-specified intervention (eg, procedure, washout, or run-in treatment including placebo run-in) Exception: A positive pregnancy test at the time of initial screening is not a reportable event.	Report all	Previously reported – Follow to completion/termination; report outcome	Within 24 hours of learning of event
Potential DILI events meeting biochemical criteria of Hy's Law (requires regulatory reporting)	Report if: – due to intervention – causes exclusion	Report - regardless of suspected etiology - to be reported as an ECI and SAE with OME criteria in the absence of other serious criteria	Previously reported – Follow to completion/termination; report outcome	Within 24 hours of learning of event

Type of Event	Reporting Period: Consent to Randomization/ Allocation	Reporting Period: Randomization/ Allocation Through Protocol-specified AE Collection Period	Reporting Period: After the Protocol- specified AE Collection Period	Time Frame to Report Event and Follow-up Information to Sponsor
ECI (requires regulatory reporting)	Report if: – due to intervention – causes exclusion	Report – requires regulatory reporting	Previously reported – Follow to completion/ termination; report outcome	Within 24 hours of learning of event
ECI (does not require regulatory reporting)	Report if: – due to intervention – causes exclusion	Report – those not requiring regulatory reporting	Not required	Within 5 calendar days of learning of event (unless an SAE)
AE=adverse event; DILI=drug-induced liver injury; ECI=event of clinical interest; NSAE=nonserious adverse event; OME=other important medical event; SAE=serious adverse event.				

8.4.2 Method of Detecting AEs, SAEs, and Other Reportable Safety Events

Care will be taken not to introduce bias when detecting AEs and/or SAEs and other reportable safety events. Open-ended and nonleading verbal questioning of the participant is the preferred method to inquire about AE occurrence.

8.4.3 Follow-up of AE, SAE, and Other Reportable Safety Event Information

After the initial AE/SAE report, the investigator is required to proactively follow each participant at subsequent visits/contacts. SAEs and other reportable safety events, including potential DILI events meeting biochemical criteria of Hy's Law, pregnancy and exposure during breastfeeding, ECIs, cancer, and overdose will be followed until resolution, stabilization, until the event is otherwise explained, or the participant is lost to follow-up (as defined in Section 7.3). The investigator will also make every attempt to follow nonserious AEs that occur in allocated participants for outcome. Further information on follow-up procedures is given in Appendix 3.

8.4.4 Regulatory Reporting Requirements for SAE

Prompt notification (within 24 hours) by the investigator to the Sponsor of SAE is essential so that legal obligations and ethical responsibilities toward the safety of participants and the safety of a study intervention under clinical investigation are met.

The Sponsor has a legal responsibility to notify both the local regulatory authority and other regulatory agencies about the safety of a study intervention under clinical investigation. The Sponsor will comply with country-specific regulatory requirements and global laws and regulations relating to safety reporting to regulatory authorities, IRB/IECs, and investigators.

Investigator safety reports must be prepared for SUSARs according to local regulatory requirements and Sponsor policy and forwarded to investigators as necessary.

An investigator who receives an investigator safety report describing an SAE or other specific safety information (eg, summary or listing of SAEs) from the Sponsor will file it along with the IB and will notify the IRB/IEC, if appropriate according to local requirements.

Note: To meet EU CTR requirements, the Sponsor will report SUSARs to the Eudravigilance database via E2B(R3) electronic ICSR form in compliance with CTR 536/2014.

8.4.5 Pregnancy and Exposure During Breastfeeding

Although pregnancy and infant exposure during breastfeeding are not considered AEs, any pregnancy or infant exposure during breastfeeding in a participant (spontaneously reported to the investigator or their designee) that occurs during the study are reportable to the Sponsor.

All reported pregnancies must be followed to the completion/termination of the pregnancy.

Any pregnancy complication will be reported as an AE or SAE.

The medical reason (example: maternal health or fetal disease) for an elective termination of a pregnancy will be reported as an AE or SAE. Prenatal testing showing fetus will be born with severe abnormalities/congenital anomalies that leads to an elective termination of a pregnancy will be reported as an SAE for the fetus.

Pregnancy outcomes of ectopic pregnancy, spontaneous abortion, missed abortion, benign hydatidiform mole, blighted ovum, fetal death, intrauterine death, miscarriage, and stillbirth must be reported as serious events (Important Medical Events). If the pregnancy continues to term, the outcome (health of infant) must also be reported.

8.4.6 Disease-related Events and/or Disease-related Outcomes Not Qualifying as AEs or SAEs

Efficacy endpoints as outlined in this section will not be reported to the Sponsor as described in Section 8.4.1.

Specifically, the suspected/actual events covered in this exception include any event that is disease progression of the cancer under study.

The Sponsor will ensure that unblinded aggregated efficacy endpoint events and safety data are monitored to safeguard the participants in the study. Any suspected endpoint that upon review is not progression of the cancer under study will be forwarded to Global Pharmacovigilance as an SAE within 24 hours of determination that the event is not progression of the cancer under study.

8.4.7 Events of Clinical Interest

Selected serious and nonserious AEs are also known as ECIs and must be reported to the Sponsor.

ECIs for this study include:

All potential DILI events meeting biochemical criteria of Hy's Law will be reported to the Sponsor, regardless of suspected etiology, as both an ECI and SAE, with OME criteria in the absence of other SAE criteria, within 24 hours of learning of the event. Potential DILI events are defined as:

- An elevated AST or ALT laboratory value that is greater than or equal to $3\times$ the ULN and,
- An elevated total bilirubin laboratory value that is greater than or equal to $2\times$ the ULN and,
- At the same time, an alkaline phosphatase laboratory value that is less than $2\times$ the ULN,

determined by way of protocol-specified laboratory testing or unscheduled laboratory testing.*

*Note: These criteria are based on available regulatory guidance documents. The purpose of the criteria is to specify a threshold of abnormal hepatic tests that may require an additional evaluation for an underlying etiology. The study-site guidance for assessment and follow up of these criteria can be found in the Investigator Study File Binder (or equivalent).

Additional ECIs for this study include:

1. An overdose of Sponsor's product, as defined in Section 8.5.

8.5 Treatment of Overdose

For this study, an overdose of MK-1308A will be defined as any dose of 62.5 mg / 1000 mg MK-1308A or greater.

For this study, an overdose of pembrolizumab will be defined as any dose of 1000 mg or greater.

For this study, an overdose of MK-4280A will be defined as any dose of 1600 mg / 400 mg MK-4280A or greater.

[figure not shown]
For this study, an overdose of MK-7684A will be defined as any dose of 600 mg / 600 mg MK-7684A or greater.

For this study, an overdose of MK-4830 will be defined as any dose of 1200 mg of MK-4830 or greater.

No specific information is available on the treatment of overdose of any of the study interventions. In the event of overdose, the participant should be observed closely for signs of toxicity. Appropriate supportive treatment should be provided if clinically indicated.

8.6 Pharmacokinetics

CCI

8.6.1 Blood Collection for PK

CCI

8.6.2 Blood Collection for ADA

CCI

8.7 Pharmacodynamics

Pharmacodynamic parameters will not be evaluated in this study.

8.8 Biomarkers

CCI

Sample collection, storage, and shipment instructions for the exploratory biomarker specimens will be in the Laboratory Manual or Procedure Document.

For participants in closed arms, biomarker samples will no longer be collected.

8.8.1 Planned Genetic Analysis Sample Collection

CCI

8.9 Future Biomedical Research Sample Collection

CCI

8.10 Medical Resource Utilization and Health Economics

Medical resource utilization and health economics data, associated with medical encounters, will be collected in the CRF by the investigator and study-site personnel for all participants throughout the study. Protocol-mandated procedures, tests, and encounters are excluded.

The data collected may be used to conduct exploratory economic analyses and will include:

- Number and duration of medical care encounters, including surgeries, and other selected procedures (inpatient and outpatient)
- Duration of hospitalization (total days or length of stay, including duration by wards [eg, intensive care unit])
- Number and type of diagnostic and therapeutic tests and procedures
- Outpatient medical encounters and treatments (including physician or emergency room visits, tests and procedures, and medications).

All-cause hospitalizations and emergency room visits must be reported in the eCRF, from the time of treatment allocation through 90 days after cessation of study intervention, or 30 days

after cessation of study intervention, if the participant initiates new anticancer therapy, whichever is earlier.

For participants in closed arms, data on medical resource use and health economics will no longer be collected.

8.11 Visit Requirements

Visit requirements are outlined in Section 1.3. Specific procedure-related details are provided in Section 8.

Refer to Section 6.1.1 for study intervention information, Section 8.2.1 for imaging information, Section 8.2.2 for PRO collection information, Section 8.3 for safety monitoring information, Section 8.6 for PK/ADA sample collection information, Section 8.8 for biomarker sample collection information, and Section 8.11.4 for posttreatment follow-up information for participants in closed arms.

8.11.1 Screening

Documented informed consent must be provided before performing any protocol-specific procedure. Results of a test performed before the participant provides documented informed consent as part of routine clinical management are acceptable in lieu of a screening test if performed within the specified time frame.

Screening procedures are to be completed within 28 days before the first dose of study intervention.

Participants may be rescreened after initially failing to meet the inclusion/exclusion criteria. Results from assessments during the initial screening period are acceptable in lieu of a repeat screening test if performed within the specified time frame and the corresponding inclusion/exclusion criteria is met. Participants who are rescreened will retain their original screening number.

8.11.2 Treatment Period

Visit requirements are outlined in the SoA (Section 1.3). Specific procedure-related details are provided in Section 8.1.

Cohort B participants on Q6W study drug dosing schedule will have a Day 22 visit at each 6-week cycle and undergo assessments as listed in the SoA (Section 1.3).

8.11.3 Participants Discontinued From Study Intervention but Continuing to be Monitored in the Study

Participants who discontinue study treatment due to disease progression or start of a new anticancer therapy will have Safety Follow-up and then proceed directly to Survival Follow-up as described in Section 8.11.4.3.

The End of Treatment Visit should occur at the time study intervention is discontinued for any reason. If the End of Treatment Visit occurs 30 days from the last dose of study intervention, at the time of the mandatory Safety Follow-up Visit, the End of Treatment Visit procedures and any additional Safety Follow-up procedures should be performed. Additional details regarding participant treatment discontinuation can be found in Section 7.1.

8.11.4 Posttreatment Visits

Participants in closed arms who complete study treatment (including Second Course, if applicable) or otherwise meet EOT criteria will be discontinued from the study after the EOT visit and any required Safety Follow-up Visit. There will be no follow-up for survival status. Participants in closed arms currently in Survival Follow-up are considered to have completed the study and therefore should obtain imaging and further oncological care as per local SOC. Participants in closed arms currently in Efficacy Follow-up will be imaged as per local SOC with no central review. Standard safety reporting should, however, continue as applicable. Participants in closed arms remaining on study should continue to be monitored in the study through the AE reporting period (Section 8.4).

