Vital Signs (temperature, HR, RR, DBP, SBP)	X	X	X	X	X	X	X			BP and pulse rate will be measured after the participant has been resting for 5 minutes. Include pulse oximetry (SpO2) if locally required.
12-lead ECG	X		X*	X*	X*	X				*As clinically indicated.
ECOG Performance Status	X	X	X	X	X	X	X			Must be performed within 3 days of C1D1 treatment and before treatment at each cycle.
AE/SAE review	X									AEs monitored up to 30 days after last dose. SAEs monitored up to 90 days and pregnancy monitored up to 120 days after last dose, or 30 days after last dose if participant starts a new anticancer therapy, whichever is sooner. Refer to Section 8.3 for safety monitoring information for participants in closed arms.
Laboratory Assessments										
Hematology/Chemistry	X	X*	X	X	X	X	X			Collect Predose. *Collect within 72 hours before first study intervention dose.
Urinalysis	X	X*	X*	X*	X*	X*	X			*As clinically indicated Collect within 72 hours before first study intervention dose.
Serum or Urine Pregnancy test (WOCBP only)	X	X		X		X	X			WOCBP require a negative test prior to allocation. If more than 24 hours for a urine test or 72 hours for a serum test have elapsed prior to the first dose of study intervention, another pregnancy test is required. See country-specific requirements in Appendix 7.

Study Period:	Screening	Intervention				EOT	Posttreatment			Notes
Visit Number/Title:	Screening	Cycle 1		Cycle 2 onwards*			Safety FU	Efficacy FU	Survival FU	*Cycles 2 to 17 for Q6W schedule; Cycle 2 to 35 for Q3W schedule.
Cycle Day	Up to 28 days prior to first dose	1	Day 22 (Q6W regimens only)	1	Day 22 (Q6W regimens only)	DC	30 days after last dose			
Scheduling Window (days):	-28 to -1	+3	±3	±3	±3		+7	Q9W ±7	Q12W ±14	
PT/INR and aPTT/PTT (baseline only)	X									Additional testing to be conducted as clinically indicated.
HIV, HBsAg, HCV	X*									*Only if required by local health authority. See country-specific requirements in Appendix 7.
Thyroid Function Tests (TSH, T3, T4), Cortisol, and ACTH**	X		X	X		X	X			Free T3 and Free T4 are acceptable if total T3 and total T4 are unavailable. After C1, retrospective review of thyroid function, ACTH and cortisol testing results is allowed when the results are not available prior to dosing. **ACTH testing is to be done as required per investigator's discretion.
Serum Tumor Marker (CEA)	X	X	X	X		X		X		Dosing permitted prior to results of CEA being known.

Study Period:	Screening	Intervention				EOT	Posttreatment			Notes

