Sponsor may elect to close an arm, the enrollment or study procedures for other arms of the study will remain unaffected. In addition, there are no current plans to add more cohorts or to expand the existing cohorts in this study. At implementation of Amendment 05, the following treatment arms are considered closed: Cohort B: MK-4280A, Cohort B: MK-7684A, and Cohort B: MK-4830+pembrolizumab.

As of the Investigator Letter dated 16-DEC-2024, participants who were receiving MK-4280A were offered the option to continue study therapy until treatment completion or transition to pembrolizumab monotherapy, and participants who were receiving MK-7684A were discontinued from that study therapy and offered the option to transition to pembrolizumab monotherapy. As per the Investigator Letter dated 25-SEP-2023, the MK-4830+pembrolizumab arm was closed to enrollment; all ongoing participants were offered the option to continue study therapy until treatment completion or transition to pembrolizumab monotherapy.

Participants who opt to continue treatment with pembrolizumab monotherapy will remain on the same visit schedule as per the initial assignment.

Participants in closed arms with access to approved SOC (eg, immunotherapy, chemotherapy, targeted therapy) should be considered for discontinuation from the study. Participants in closed arms who are benefiting from pembrolizumab monotherapy, but unable to access it as SOC outside the study, may continue on study and receive treatment with pembrolizumab monotherapy until discontinuation criteria are met. The final required study visit will be the Safety Follow-up Visit.

Participants will be evaluated with tumor scans and RECIST 1.1 response assessment (chest, abdomen, and pelvis) Q9W (63 ± 7 days) from the date of allocation until disease progression is assessed by the site and verified by BICR or initiation of a new anticancer treatment. All scans obtained will be assessed by the BICR using RECIST 1.1 for determination of ORR and PFS. Refer to Section 8.2.1 for imaging information for participants in closed arms.

Survival follow-up will continue after disease progression is verified by BICR or the start of new anticancer treatment for participants in open arms. In addition, upon Sponsor request, participants may be contacted for survival status at any time during the study. Refer to Section 8.11.4 for posttreatment follow-up information for participants in closed arms.

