8.3 Safety Assessments

Details regarding specific safety procedures/assessments to be performed in this study are provided. The total amount of blood/tissue to be drawn/collected over the course of the study (from prestudy to poststudy visits), including approximate blood/tissue volumes

drawn/collected by visit and by sample type per participant, can be found in the Laboratory Manual or Procedure Document.

Planned time points for all safety assessments are provided in the SoA.

Participants in closed arms who complete study treatment (including Second Course, if applicable) or otherwise meet EOT criteria will be discontinued from the study after the EOT visit and any required Safety Follow-up Visit.

Participants in closed arms remaining on study should continue to be monitored in the study through the AE reporting period (Section 8.4).

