8.11.4.1 Safety Follow-up Visit

The mandatory Safety Follow-up Visit should be conducted approximately 30 days after the last dose of study intervention or before initiation of a new anticancer treatment, whichever comes first.

Participants who are eligible for retreatment with MK-1308A or pembrolizumab monotherapy may have up to 2 safety follow-up visits: 1 after the Initial Treatment or First Course and 1 after the Second Course.

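### Closed-arm participants leave the study at about day 30, but the 90-day SAE window still applies to them, and the protocol does not say which rule prevails or how SAEs are ascertained in between.

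*Combined protocol and SAP*

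**What the plan says.** **Exit from the study.** Section 8.11.4 says that closed-arm participants who complete treatment or otherwise meet end-of-treatment criteria "will be discontinued from the study after the EOT visit and any required Safety Follow-up Visit". Section 8.3 and the Synopsis give the same rule. For closed-arm participants who stay on pembrolizumab monotherapy, Sections 4.1 and 6.1.1.1 add: "The final required study visit will be the Safety Follow-up Visit". On timing, Section 8.11.4.1 says: "The mandatory Safety Follow-up Visit should be conducted approximately 30 days after the last dose of study intervention", or before a new anticancer treatment if that comes first. Table 2 allows +7 days.

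**SAE reporting.** Section 8.4.1 requires SAEs to be reported "from the time of intervention allocation through 90 days after cessation of study intervention", shortened to 30 days if new anticancer therapy starts. The Cohort B schedule (Table 2) agrees: "SAEs monitored up to 90 days and pregnancy monitored up to 120 days after last dose". Neither place gives closed arms a shorter period; Table 2 refers to Section 8.3 for them.

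**Monitoring after closure.** Section 8.3, repeated in Section 8.11.4, says: "Participants in closed arms remaining on study should continue to be monitored in the study through the AE reporting period". Section 8.11.4 also says that standard safety reporting continues as applicable.

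**Former participants.** Section 8.4.1 says: "Investigators are not obligated to actively seek AEs or SAEs or other reportable safety events in former study participants". After discharge, an SAE must be notified only if the investigator learns of it and considers it reasonably related.

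**Participants in Survival Follow-up.** Section 8.11.4 treats closed-arm participants already in Survival Follow-up as having completed the study.

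**The concern.** A participant discharged at the Safety Follow-up Visit is no longer on study in the ordinary sense, so the sentence on continued monitoring does not plainly cover them. The sentence on former participants plainly might. A site could then close the record at about day 30 while the 90-day SAE obligation is still running.

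This matters because Section 6.6.1 warns that immune-related events may appear several months after the last dose. Safety relative to pembrolizumab remains a Cohort B secondary objective, and Section 9.6.2 plans 95% confidence intervals for between-arm differences in SAEs that reach 5% in a treatment group. If late SAEs are picked up differently in closed and open arms, part of any difference could reflect ascertainment.

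Two further provisions remove routes by which such events might have come to light:

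- Section 8.10 collects hospitalizations and emergency visits to day 90 (day 30 with new therapy), but stops this collection in closed arms.
- Section 8.11.3 moves participants who progress straight from Safety Follow-up to Survival Follow-up. A closed-arm participant can therefore be in Survival Follow-up before day 90, and so be declared complete with the SAE window open.

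**Working it through.** The plan states no figure to reproduce. The check compares time windows and then reads the passages together.

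**Inputs**

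- Last required closed-arm visit: day 30 after the last dose (Section 8.11.4.1), day 37 at the end of the +7-day window (Table 2).
- End of the SAE window: day 90 (Section 8.4.1, Table 2), or day 30 if new anticancer therapy starts.
- First survival contact for participants who do not enter Efficacy Follow-up: 12 weeks after the later of the End of Treatment and Safety Follow-up Visits (Section 8.11.4.3).
- Survival contact in closed arms: none (Section 8.11.4).

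**Part of the SAE window without a scheduled contact**

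Gap = end of SAE window − day of last required visit.

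| Case | Calculation | Gap | Share of 90 days |
|---|---|---|---|
| Visit on day 30 | 90 − 30 | 60 days | 60/90 = 67% |
| Visit on day 37 | 90 − 37 | 53 days | 53/90 = 59% |
| 30-day limit applies (new therapy) | 30 − 30 | about 0 days | – |

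**Open-arm comparison**

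Open-arm participants who go straight to Survival Follow-up have a first contact at about day 30 + 84 = 114. That is after the SAE window closes, so it could recover a day 31 to 90 event only retrospectively. Those in Efficacy Follow-up continue to be seen every 9 weeks (Section 8.11.4.2).

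**Reading the passages together**

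1. Sections 8.3 and 8.11.4 end study participation after the day-30 visit.
2. Section 8.4.1 keeps the reporting duty "through 90 days after cessation of study intervention or 30 days after cessation of study intervention if the participant initiates new anticancer therapy", without mentioning closed arms.
3. The bridging sentence in Sections 8.3 and 8.11.4 depends on being on study, the status that step 1 has just ended.
4. The statement that standard safety reporting continues follows the sentence on closed-arm participants in Efficacy Follow-up. It does not say whether step 1 or step 2 governs.
5. No sentence says whether a participant discharged at day 30 counts as a former participant for Section 8.4.1.

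Steps 1 and 2 are therefore not reconciled, and steps 3 to 5 do not settle the matter.

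**The case against.** The strongest reply is that the 90-day duty is never withdrawn. Sections 4.1 and 6.1.1.1 limit visits, not reporting. Discontinuation comes after the visit, which need not mean on that day. Sections 8.3 and 8.11.4 both point back to Section 8.4. On this reading there are no further visits but SAE reporting runs to day 90. That is coherent, and it may be what the sponsor intends. The text does not say so, however, and a site that follows the former-participant sentence would also be within the wording. It is therefore too strong to say that late SAEs are no longer sought.

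Other objections stand and limit the point:

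- A reader might infer that open-arm SAEs are actively sought after day 30. Section 8.11.4.2 describes imaging and disease status, and Section 8.11.4.3 describes survival status; neither assigns SAE enquiry to those contacts. A difference between arms is possible but not shown.
- A reader might infer that active pregnancy follow-up is lost. Posttreatment pregnancy reporting is spontaneous in every arm (Synopsis, Section 8.4.5), so closure removes no active enquiry.
- A reader might see special significance in MK-7684A, which was stopped for an unfavorable risk-benefit balance. The Synopsis and Section 2.3 say that the stop was not based on safety concerns, and Section 2.3 cites lack of efficacy.
- A reader might infer that safety comparisons would flatter the closed arms. No count of affected participants or late SAEs is given, part of Section 9 is redacted, and the Tier 2 safety intervals are described as descriptive. Neither direction nor size can be stated.
- A day-90 call in closed arms alone could create the opposite imbalance. This is a fair criticism of such a fix.

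**Conclusion.** The point holds as an unreconciled safety-collection rule that should be corrected. Taken literally, the protocol leaves 53 to 60 days of the 90-day SAE window with no scheduled contact and no clear duty to ask, in three of the five Cohort B arms. Late-SAE ascertainment could therefore differ from that in the MK-1308A and pembrolizumab arms.

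This rests on three assumptions: the Safety Follow-up Visit takes place between day 30 and day 37, no new anticancer therapy has shortened the window to 30 days, and the participant's SAE window was still open when the closed-arm rules took effect. The documents do not say how many participants meet these conditions, so the effect on any safety comparison is unknown. ORR by BICR, the primary endpoint, is not affected.

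**What to change.** Amend Sections 8.3 and 8.11.4 and the Synopsis, and align Sections 4.1 and 6.1.1.1, to state that:

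1. the Section 8.4.1 reporting periods apply to closed-arm participants regardless of when the last visit took place;
2. discontinuation from the study takes effect only when the SAE reporting period ends, including for closed-arm participants in Survival Follow-up whose window was still open at closure;
3. SAEs between the Safety Follow-up Visit and the end of the window are ascertained by a named method, for example one telephone contact at the end of the SAE window, with SAE enquiry made in the same way in the open arms.

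The cost is amendment wording and about one call per affected participant. No visit, scan or sample is added.
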